## Table 4-4 Abnormal criteria

Laboratory Variable (unit)	Criteria
Albumin (g/L)	<lln< td=""></lln<>
Bilirubin (direct/conjugated)	>ULN
(umol/L))	>2xULN
Gamma Glutamyltransferase (GGT)	>ULN
(U/L)	>3xULN
Glucose (mmol/L)	>ULN
Cholesterol (HDL) (mmol/L)	>ULN
Cholesterol (LDL) (mmol/L)	>ULN
SGOT (AST) (U/L)	>ULN
	>2xULN
	>3xULN
	>5xULN
SGPT (ALT) (U/L)	>ULN

Protocol No. CFTY720D2312

	>2xULN
	>3xULN
	>5xULN
Cholesterol (total) (mmol/L)	>ULN

## 8.2.3 Data Summaries for lab tests

All lab parameters (excluding all hematology % values except % for white cell differential values) will be summarized.

Summaries on the safety set by treatment group include:

- Summary statistics of lab results (hematology, biochemistry, and urinalysis) by visit
- Changes from baseline in lab results (hematology, biochemistry, and urinalysis) by visit
- Summary statistics of percent of baseline in hematology results by visit
- Incidence rates of newly occurring or worsening abnormalities based on clinically notable laboratory abnormality criteria (based on criteria in Table 4-2)
- Incidence rates of clinically notable laboratory abnormalities by visit
- Incidence rates of laboratory results meeting abnormal criteria (in Table 4-4) by visit
- Frequency (%) distributions of liver function test results and hematology results in predefined categories (as specified in the table shells)
- Shift table (low, normal, or high as defined by the normal ranges) from baseline to post-baseline extreme values in hematology, biochemistry and continuous urinalysis results
- Shift table (negative, +, 2+, 3+, or 4+) from baseline to post-baseline extreme values in urinalysis results
- Frequency (%) distributions of serology results for subjects with serology test

Summaries on the follow-up set by treatment group include:

- Summary statistics of lab parameters (hematology, biochemistry, and urinalysis) by visit
- Change from baseline in lab parameters (hematology, biochemistry, and urinalysis) by visit

## 8.3 Vital signs

## 8.3.1 Vital signs measurements

The vital sign CRF collects systolic blood pressure (SBP) and diastolic blood pressures (DBP), pulse, body temperature, and body weight. The mean arterial blood pressure will be derived from the DBP and SBP using the formula below

• Mean arterial blood pressure = [2\*DBP + SBP]/3.

Before the protocol amendment 1, the CRF collects vital signs only at sitting position at each visit. After the protocol amendment 1, the CRF collects vital signs at supine and standing position at each visit

For all visits (excluding the first or second or restart dose monitoring data) one measurement of pulse and 3 measurements of blood pressure (SBP and DBP) are collected before the protocol amendment 1 and three measurements of pulse and blood pressure (SBP and DBP) are collected.

At first or second or restart dose monitoring, pulse, SBP and DBP are measured 3 times at the scheduled pre-dose time point. The average of available values among three pulse ( or SBP or DBP) measurements at the same position will be calculated.

For post-baseline assessments (excluding the first or second or restart dose monitoring data), the pulse or blood pressure value will be the average of the non-missing values of the 3 measurements, if it is not a single measurement, at the same position. If more than one blood pressure assessment after the average of the 3 measurements at the same position at the same date (scheduled or unscheduled, except for the first dose or second dose or restart dose monitoring data) exists in a particular visit as defined by the visit windows, the blood pressure value will be the average of all assessments at the same position.

The vital sign (pulse, SBP and DBP) during the first dose administration on Day 1 or Day 2 and restart data will not be put into visit windows, but will be summarized separately by the hour in which the measurement was reported.

## 8.3.2 Vital signs notable criteria

Clinical notable criteria in vital signs are summarized in Table 4-5.

Table 4-5 Criteria for clinically notable vital signs

Vital Sign Variable	Notable Criteria
Pulse (beats/min)	>120bpm or Increase of ≥15 bpm from baseline
	or
	< 50bpm or Decrease of ≥15 bpm from baseline
Systolic BP (mmHg)	≥160 mm Hg or Increase of ≥20 mm Hg from baseline
	or

Protocol No. CFTY720D2312

	≤ 90 mm Hg or Decrease of ≥ 20 mm Hg from baseline
Diastolic BP (mmHg)	≥ 100 mmHg or Increase of ≥ 15 mm Hg from baseline
	or
	≤ 50 mmHg or Decrease of ≥ 15 mm Hg from baseline
Temperature (°C)	>38.3 °C/101°F
Body weight (kg)	+ > 7% from baseline weight

## 8.3.3 Data summaries for vital signs

Pulse and blood pressure will be reported separately for sitting, supine and standing position. Incidence rates of clinically notable, post-baseline abnormalities and orthostatic hypotension will be provided by treatment. Orthostatic hypotension is defined as a reduction of systolic blood pressure of at least 20 mm Hg or diastolic blood pressure of at least 10 mm Hg from supine to standing position.

The following summaries will exclude hourly vital sign data from the first dose or second dose or restart dose monitoring.

Summaries on the safety set by treatment group include:

- Summary statistics of vital sign parameters by visit
- Changes from baseline in vital sign parameters by visit
- Frequency (%) distributions of highest SBP, DBP, and lowest pulse in pre-defined categories respectively
- Incidence rates of notable vital sign abnormalities based on the notable criteria in Table 4-5
- Incidence rates of orthostatic hypotension by treatment and visit

Summaries on the follow-up set by treatment group include:

- Summary statistics of vital sign parameters by visit
- Change from baseline of vital sign parameters by visit

## 8.4 Electrocardiograms (ECG)

The ECG data includes quantitative variables such as ventricular rate, PQ or PR interval, R-R interval, QRS duration, and uncorrected QT interval as well as categorical variables such as ECG interpretation (normal or abnormal), ECG evaluation type (rhythm, conduction, etc) and ECG findings (prolonged QTc, low voltage, etc).

#### 8.4.1 Corrected QT interval

The uncorrected QT interval will be corrected using the Bazett and Fridericia formulas. The Bazett formula corrects the QT interval by dividing by the square root of the R-R interval (secs). The Fridericia formula corrects the QT interval by dividing by the cubic root of the R-R interval (secs).

## 8.4.2 Abnormality criteria for corrected QT interval

Abnormality criteria for the corrected QT interval (Bazett and Fridericia) are listed in Table 4-6.

Table 4-6 Abnormality criteria for corrected QT interval

	Male Subjects	Female Subjects
1	>450 msec	>470 msec
2	>500 msec	>520 msec
3	30 - 60 msec increase from Baseline	
4	>60 msec increase from Baseline	

## 8.4.3 ECG findings

ECG findings are associated with the ECG evaluation type and thus will be summarized by the ECG evaluation type.

#### 8.4.4 Data summaries for ECG data

The following summaries will exclude ECG data from the first dose or second dose or restart dose monitoring.

Summaries on the safety set by treatment group include:

- Summary statistics of quantitative ECG parameters by visit
- Changes from baseline in quantitative ECG parameters by visit
- Incidence rates of abnormal corrected QT interval (Bazett and Fridericia) as defined by the abnormality criteria in Table 4-6
- Frequency (%) distribution of ECGs interpretation (normal/abnormal) by visit
- Frequency (%) distribution of ECG findings by ECG evaluation type by visit

Note: For this study the only post-baseline visit is Month 12/EOT (end of treatment). So, all summaries above will be present for Baseline and then Month 12/EOT.

## 8.5 Pulmonary function tests (PFT)

#### 8.5.1 Predicted values and units of PFTs

For each subject, the predicted values of the PFT parameters (Forced expiratory volume in 1 second (FEV1), Forced vital capacity (FVC), FEV1/FVC, and Diffusion capacity of carbon monoxide (DLCO)) will be calculated based on the formulas below.

## Reference equations to calculate the predicted values of FEV1, FVC, FEV1/FVC

Forced expiratory volume in one second (FEV1) (Unit: Liter/second):

```
male: (4.3 \cdot \text{height (m)}) - (0.029 \cdot \text{age (yr)}) - 2.49 [\pm 0.51]
female: (3.95 \cdot \text{height (m)}) - (0.025 \cdot \text{age (yr)}) - 2.6 [\pm 0.38]
```

Forced vital capacity (FVC) (Unit: Liter):

```
male: (5.76 \cdot \text{height (m)}) - (0.026 \cdot \text{age (yr)}) - 4.34 [\pm 0.61]
female: (4.43 \cdot \text{height (m)}) - (0.026 \cdot \text{age (yr)}) - 2.89 [\pm 0.43]
```

FEV1/FVC (Unit: %):

```
male: -0.18 \cdot age (yr) + 87.21 [\pm 7.17]
female: 0.19 \cdot age (yr) + 89.10 [\pm 6.51]
```

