4.1 Inclusion criteria

Patients eligible for inclusion in this study have to fulfill all of the following criteria:

- 1. Written informed consent must be obtained before any assessment is performed
- 2. Male and female patients 18 to 65 years of age, inclusive
- 3. Patients with RRMS, as defined by 2010 revised McDonald criteria (Appendix 2)
- 4. Patients must be neurologically stable with no onset of relapse within 30 days of randomization
- 5. Patients with at least 1 documented relapse during the previous year or 2 documented relapses during the previous 2 years before randomization
- 6. Patients with an Expanded Disability Status Scale (EDSS) score of 0 to 6.0, inclusive, at Screening. A score of 6.0 indicates unilateral assistance (cane or crutch) required to walk at least 100 meters with or without resting.

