The FEV_1 describes the volume (in Liters) that is expelled within one second of forced expiration after a maximal inspiration and reflects the large airway resistance. A decrease in FEV_1 serves as a good parameter for detection of an obstructive ventilatory defect.

Forced vital capacity (FVC):

The FVC denotes the volume of gas (in Liters) which is exhaled during a forced expiration starting from a position of full inspiration and ending at complete expiration. This parameter

is normal or might be slightly decreased in obstructive disease but shows a mild to severe decrease in restrictive disease.

Page 64

Diffusion capacity of carbon monoxide (D_I CO):

Gas exchange is assessed by the D_ICO evaluated by the single breath holding method. It is a measurement of carbon monoxide (CO) transfer from the lung to pulmonary capillary blood over a breath-holding period. Due to ability of CO to bind to hemoglobin, the diffusion capacity needs to be corrected for hemoglobin to reflect an altered lung gas transport rather than altered hemoglobin.

The average of at least 2 acceptable tests that meet the repeatability requirement of either being with 3 mL CO/min/mm Hg (or 1 mmol/min/kPa) of each other or being within 10% of the highest value should be reported.

A D_ICO test is acceptable if it fulfills all the following criteria:

- Use of proper quality-controlled equipment
- Inspired volume of greater than 85% of largest vital capacity in less than 4 seconds
- A stable calculated breath hold for $10 (\pm 2)$ seconds. There should be no evidence of leaks or Valsalva or Mueller maneuvers
- Expiration in less than 4 seconds (and sample collection time less than 3 seconds), with appropriate clearance of dead space and proper sampling/analysis of alveolar gas

All values must be corrected for hemoglobin concentration in the study.

The D_LCO is usually expressed in European CI conventional units: mL CO/min/torr (or mL CO/min/mm Hg), whereas the US mainly uses SI units: mmol CO/min/kPa (Conversion factor: SI units \times 2.986 = CI units).

6.5.10 **Dermatological examination**

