## Reference equations to obtain predicted values of DLCO

Single breath diffusion capacity (DLCO) (Unit: ml/min/mmHg):

```
Male: (0.3319 \cdot \text{height (cm)}) - (0.1971 \cdot \text{age (yr)}) - 18.006
Female: (0.2441 \cdot \text{height (cm)}) - (0.1436 \cdot \text{age (yr)}) - 8.20
```

In the above calculations, the height of a subject is from the screening visit and the age should be calculated based on the date when he or she performs the PFTs.

For DLCO, three units may be collected in the CRFs, which are ml/min/torr, ml/min/mmHg, and mmol/min/kpa. The PFT tables and listings will use the unit ml/min/mmHg. The other two units will be converted to ml/min/mmHg, prior to any calculations, as follows:

- 1 ml/min/torr = 1 ml/min/mmHg;
- 1 mmol/min/kpa = 2.986 ml/min/mmHg.

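### As read, the SAP's predicted FEV1/FVC for women rises with age and exceeds 100% from age 58, so women's percent-predicted values would be too low if coded as printed

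*SAP*

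**What the plan says.** SAP Section 8.5.1 states that predicted values of FEV1, FVC, FEV1/FVC and DLCO "will be calculated based on the formulas below", so the printed equations are the calculation rule. For FEV1/FVC in % they are:

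- men: "male: -0.18 \cdot age (yr) + 87.21"
- women: "female: 0.19 \cdot age (yr) + 89.10"

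The same block gives women's FEV1 as "female: (3.95 \cdot \text{height (m)}) - (0.025 \cdot \text{age (yr)}) - 2.6" and women's FVC as "female: (4.43 \cdot \text{height (m)}) - (0.026 \cdot \text{age (yr)}) - 2.89". The text after the DLCO equations adds that "the age should be calculated based on the date when he or she performs the PFTs".

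Section 8.5.2 defines percent predicted as 100 times observed over predicted. Section 8.5.3 lists percent-predicted FEV1/FVC and its change from baseline by visit, on both the safety set and the follow-up set. Protocol Section 9.5.2 treats an FEV1/FVC below 80% of predicted as abnormal. Protocol Section 4.1 admits "Male and female patients 18 to 65 years of age, inclusive".

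**The concern.** The predicted value is the denominator of percent predicted. A female line that rises with age makes that denominator too large, by more the older the woman, and eventually gives a value that cannot occur. Protocol Section 6.5.9 says FEV1 "describes the volume (in Liters) that is expelled within one second of forced expiration" and defines FVC as the whole volume of the forced expiration, so FEV1/FVC cannot exceed 100%.

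If the line was programmed as printed, women's percent-predicted FEV1/FVC would look spuriously low, increasingly so with age, and changes from baseline would be compressed. Any application of the protocol's 80%-of-predicted rule to FEV1/FVC would be distorted as well.

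**Working it through.** The documents give no worked value to reproduce, so the check evaluates the printed equations.

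**Inputs.** All equations are from SAP Section 8.5.1 and the age range is from Protocol Section 4.1. The documents give no distribution of height. I assume 1.65 m for women (range 1.55 to 1.75 m) and 1.68 to 1.88 m for men.

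**Where the printed line passes 100%.** 0.19 × age + 89.10 = 100 gives age = 10.90 / 0.19 = 57.4. At 58 the prediction is 100.12% and at 65 it is 101.45%.

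**Comparison with two benchmarks.**

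- A: the same line with a minus sign, -0.19 × age + 89.10.
- B: the SAP's own female equations divided, 100 × FEV1 / FVC at 1.65 m. At 40, FEV1 = 3.95 × 1.65 - 0.025 × 40 - 2.6 = 2.9175 and FVC = 4.43 × 1.65 - 0.026 × 40 - 2.89 = 3.3795, a ratio of 86.3%.

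| Age | Printed | A | B | Printed - B | B - A |
|---|---|---|---|---|---|
| 18 | 92.5 | 85.7 | 87.8 | 4.8 | 2.1 |
| 40 | 96.7 | 81.5 | 86.3 | 10.4 | 4.8 |
| 50 | 98.6 | 79.6 | 85.5 | 13.1 | 5.9 |
| 65 | 101.5 | 76.8 | 84.0 | 17.5 | 7.2 |

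Benchmark B falls with age, and at 65 it is 83.0% for 1.55 m and 84.7% for 1.75 m. The printed line therefore contradicts the SAP's own female equations in direction and lies well above them.

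Benchmark A has the right direction and is closer to B, but it lies below B by 2.1 to 7.2 points. For men, the ratio of the SAP's FEV1 and FVC equations exceeds the male FEV1/FVC line by only 0.3 to 3.2 points over ages 18 to 65. The check therefore rejects the rising slope without proving that -0.19 was intended.

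**Signs.** The age coefficients in the FEV1, FVC, FEV1/FVC and DLCO equations are -0.029, -0.025, -0.026, -0.026, -0.18, -0.1971 and -0.1436, plus this one at +0.19.

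**Effect on percent predicted.** A woman exactly at her expected value is reported at 100 × benchmark / printed:

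| Age | Against A | Against B |
|---|---|---|
| 18 | 92.6% | 94.8% |
| 40 | 84.3% | 89.3% |
| 50 | 80.7% | 86.7% |
| 65 | 75.7% | 82.8% |

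Heights of 1.55 to 1.75 m move the B column by about 1 point or less.

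**Effect on change from baseline, age held fixed.** The shrinkage is 1 - benchmark / printed: 5% to 7% at 18, 11% to 16% at 40 and 17% to 24% at 65. For example, a 5-point fall in the ratio at 40 shows as -500 / 96.7 = -5.2, where B gives -500 / 86.3 = -5.8 and A gives -500 / 81.5 = -6.1.

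**Effect on change from baseline, one year of ageing.** Because age is recalculated at each test, the Month 12 distortion is smaller. For a 5-point fall from the benchmark value it is about 1% at 18, 6.5% (B) to 10% (A) at 40 and 13% (B) to 19% (A) at 65. A 40-year-old woman whose ratio does not change shows a fall of about 0.2 points, where A gives a rise of 0.23 and B a rise of 0.09.

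**The case against.** The strongest objection is that everything hangs on one character in a text extracted from PDF. The extraction is imperfect elsewhere: in SAP Section 12.1.1 the same variable name appears in two spellings, and the SAP's body-weight criterion shows a plain plus where Protocol Appendix 1 has plus-or-minus. An isolated positive sign among eight age terms fits a lost character as well as an author's slip. This stands as a real possibility. The minus on the male line directly above did survive, but that is weak evidence about its neighbour.

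The second objection is reach, and it also stands. Absolute FEV1/FVC is tabulated alongside percent predicted. The shift tables, the counts below 80% and 60% of baseline and the relevant-change table in Section 8.5.3 cover FEV1, FVC and DLCO only. The action thresholds in Protocol Appendix 3 use percent of baseline. No table listed in Section 8.5.3 counts the protocol's 80%-of-predicted rule for FEV1/FVC. The error is the same function of age in every arm.

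The third objection is that neither benchmark is an established truth. That is so, and it is why the sizes are given as ranges. The direction does not depend on the choice, because the printed denominator is too large against both.

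**Conclusion.** The point holds as a conditional one. As read, the female FEV1/FVC equation is wrong: it predicts an impossible value from age 58 and contradicts the SAP's own female FEV1 and FVC equations. If it was coded as printed, women's percent-predicted FEV1/FVC is too low by about 5 to 7 points at age 18, 11 to 16 at 40 and 17 to 24 at 65 for a woman at her expected value.

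The sizes assume that the sign is real, that the program follows the page, and that one of the two benchmarks (B at 1.65 m) is a fair stand-in for the intended equation. Men, the other lung-function parameters, absolute values and all efficacy analyses are unaffected. The table shells (RAP Module 7.1) were not available, so a categorised FEV1/FVC output there cannot be excluded. The correction should be made, but it does not bear on the trial's main conclusions.

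**What to change.** Check three things: the sign on the original SAP page, the published source of the reference equations (Section 8.5.1 names none), and the line in the analysis program.

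- If the original page shows a minus and the program matches, nothing further is needed.
- If the plus sign is confirmed, restore the source equation in the SAP and cite the source. By the pattern of the male line it is probably -0.19 × age + 89.10, but the documents alone do not establish this.
- If the program used the plus sign, rerun the percent-predicted FEV1/FVC summaries and changes from baseline for women on the safety and follow-up sets, with any RAP Module 7.1 table that uses them.

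The cost is a check of one formula and, at most, a one-line correction and a small rerun.

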## Reference equations to obtain predicted values of DLCO

Single breath diffusion capacity (DLCO) (Unit: ml/min/mmHg):

```
Male: (0.3319 \cdot \text{height (cm)}) - (0.1971 \cdot \text{age (yr)}) - 18.006
Female: (0.2441 \cdot \text{height (cm)}) - (0.1436 \cdot \text{age (yr)}) - 8.20
```

In the above calculations, the height of a subject is from the screening visit and the age should be calculated based on the date when he or she performs the PFTs.

For DLCO, three units may be collected in the CRFs, which are ml/min/torr, ml/min/mmHg, and mmol/min/kpa. The PFT tables and listings will use the unit ml/min/mmHg. The other two units will be converted to ml/min/mmHg, prior to any calculations, as follows:

- 1 ml/min/torr = 1 ml/min/mmHg;
- 1 mmol/min/kpa = 2.986 ml/min/mmHg.

## 8.5.2 Percent predicted PFTs

The percent predicted PFT value, for each subject, is defined as (absolute PFT value / predicted PFT value) \* 100.

The change from baseline in percent predicted PFT value is defined as (post-baseline percent predicted PFT value - baseline percent predicted PFT value).

The percent of baseline in absolute value of a PFT is calculated as (post-baseline absolute PFT value / baseline absolute PFT value) \* 100.

The percent predicted PFT value will be categorized by pre-defined intervals. Details will be specified in the table shell document (RAP Module 7.1)

Relevant PFT changes are defined as below 80% of baseline and below 60% of baseline in absolute PFT values at 2 consecutive visits.

For non by-visit summaries, visits defined by visit windows will not be used. All available data from scheduled and unscheduled visits will be considered when checking 2 consecutive visits.

#### 8.5.3 Data summaries for PFTs

Summaries on the safety set by treatment group include:

- Summary statistics in absolute values of FEV1, FVC, FEV1/FVC, and DLCO and in percent predicted values of FEV1, FVC, FEV1/FVC, and DLCO by visit
- Changes from baseline in absolute values of FEV1, FVC, FEV1/FVC, and DLCO and in percent predicted values of FEV1, FVC, FEV1/FVC, and DLCO by visit
- Number (%) of subjects meeting the following criteria as compared to the baseline (separately for FEV1, FVC, DLCO): below 80% at any visit; below 80% at 2 consecutive visits; below 60% at any visit; and below 60% at 2 consecutive visits
- Shift tables from baseline to the lowest post-baseline values in pre-defined categories of the percent predicted values of FEV1, FVC, and DLCO
- Number (%) of subjects with relevant PFT changes (for FEV₁, FVC, and DLCO) by baseline percent predicted PFT categories

Summaries on the follow-up set include:

- Summary statistics in absolute values of FEV1, FVC, FEV1/FVC, and DLCO and in percent predicted values of FEV1, FVC, FEV1/FVC, and DLCO by visit
- Change from baseline in absolute values of FEV1, FVC, FEV1/FVC, and DLCO and in percent predicted values of FEV1, FVC, FEV1/FVC, and DLCO by visit

**Note:** Site had 5 subjects with unrealistic values (>80L) reported for FEV1/FVC in the CRF. The site is not responsive. On August 22nd, 2018, the study team reviewed the issue and agreed to set them as missing (unknown) in the analysis.

## 8.6 Ophthalmic evaluations

The ophthalmic evaluation includes assessment of visual acuity, assessment of optical coherence tomography (OCT), fluorescein angiography, and assessment of macular edema.

For the assessment of visual acuity, if the decimal score is not available but the Corrected Snellen equivalent is available, the decimal score will be calculated by division (e.g., Corrected Snellen equivalent = 10/20 infers that decimal score = 0.5). All decimal scores will be converted to the LogMAR (log of the minimum angle of resolution) equivalent by taking the negative of the common logarithm (i.e.,  $-\log_{10}$  (decimal acuity score)) (Holladay 1997). Summaries of the visual acuity will be performed on the converted scores (i.e., LogMAR equivalent).

If two or more visual acuity values for the same eye of a subject are available at a post-baseline visit window, the worst of all values will be used in the summaries. Note that the worst value for visual acuity refers to the smallest value in the decimal score (or equivalently refers to the largest value in the logMAR scale).

Visual acuity and change from baseline in visual acuity will be categorized by pre-defined intervals. Details will be specified in the table shell document (RAP Module 7.1).

The central foveal thickness (CFT), macular volume data from OCT and fluorescein angiography data will be displayed in listings.

